### a. Brief Summary

The purpose of this study is to assess the safety and ease of use of a trocar placement access device (TPAD, Tautona) for laparoscopic surgery. 10 patients will undergo laparoscopic surgery as planned, with their surgeon using the TPAD device to guide Veress needle insertion and primary trocar placement while gaining access to the peritoneal cavity. Surgeons will complete a questionnaire following use of the TPAD to evaluate the device feasibility. Ten patients will undergo standard of care without use of the TPAD device and also complete surveys.

---

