### a. Procedures

Surgeons will identify patients scheduled to undergo laparoscopic surgery procedures and notify study staff. The patient will be met in the pre- operative holding area and informed consent will be obtained.

Patients will be randomized via block randomization.

Clinical information will be collected from participating patients including age, sex, demographic, past medical and surgical history, medications, allergies, diagnosis, and planned procedure. Clinical data will be de- identified and stored on a password protected spreadsheet on a PHI- safe server.

The surgeon will utilize the TPAD device to assist with Veress needle insertion (standard of care) to obtain access to the peritoneal cavity. The device will also be used to guide primary trocar placement.

Following induction of general anesthesia, the patient is prepped and draped in sterile fashion. Local anesthetic is infiltrated at the planned incision site and an incision is made with a scalpel. These steps are the same in any laparoscopic procedure. Next, the sterile TPAD, which is connected to a suction source, is centered over the incision, and the suction cups activated to non-invasively grasp the skin. The TPAD is pulled upward, and the Veress needle is advanced through the incision into the peritoneal cavity. Once the needle enters the cavity, the abdomen is insufflated as per usual standard of care. Once insufflated, the veress needle is withdrawn while maintaining the TPAD's suction on the skin. The primary trocar is then advanced through the incision into the abdominal cavity. The suction is then released and the TPAD taken away from the operating field.

The time needed to obtain laparoscopic access and the time needed for trocar placement will be recorded. Non-identifiable photos and/or video may be taken of the TPAD device during use. Acquired digital images may capture a portion of the patient's skin, however if a patient has any identifying features such as scars or tattoos, these areas will be cropped out of the images, or if this is not possible, no images will be recorded of that patient. There will be no other alterations to the planned surgery and it will proceed as planned. Following surgery, the surgeon will complete a questionnaire. Any adverse events will be recorded by medical record review.

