**g. Study Endpoint(s)**

The study will terminate after 10 patients have been enrolled and have undergone surgery with use of the study device and 10 patients have undergone the standard of care and completed the survey. The primary outcome measure is device feasibility as measured by a surgeon questionnaire, which is completed at the end of every surgery. Secondary outcome measures include the time needed to obtain laparoscopic access using the device, as well as monitoring for adverse events. Another secondary outcome measure includes patient questionnaire to assess satisfaction.

If there is clear evidence of a lack of device feasibility through surgeon questionnaire review, or if there are any adverse events recorded that are related to the device and which endanger the health of a patient, the project leader will evaluate this information and decide whether any modifications or termination of the protocol are indicated.

---

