Pilot Study to Establish Safety and Ease of Use of a TauTona Pneumoperitoneum Assist Device (TPAD) for Laparoscopic Surgery

NCT04392635

August 19, 2024

Statistical Analysis Plan

Statistical Methods

For surgeon and patient questionnaire answers, a Wilcoxon test will be performed for each answer against a theoretical median of 4.0 (best). Since the insertion of the Veress needle should not significantly impact the final outcome of the entire laparoscopic procedure, analysis assumes that the theoretical median for each answer should be 4.0. Further, the standard of care is assumed to provide the current best care, so its theoretical median should be 4.0.

Determination of Sample Size

There were no statistically powered sample size requirements for this study. Based on the end points, the sample size of 15 for each group would be sufficient to determine bruising and the ability of the TPAD device to function as intended as compared to the control group.

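### The SAP's only test sets each answer against an assumed best score of 4.0, so the plan contains no valid comparison of TPAD with its randomised control arm

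*SAP*

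**What the plan says.** **Design.** Protocol section 2a (Procedures) states: "Patients will be randomized via block randomization". Section 1a (Brief Summary) adds a surveyed control group: "Ten patients will undergo standard of care without use of the TPAD device and also complete surveys". Section 2g (Study Endpoint(s)) defines the primary outcome for both arms: "The primary outcome measure is device feasibility as measured by a surgeon questionnaire, which is completed at the end of every surgery". The secondary outcomes there are access time, adverse events and a patient satisfaction questionnaire.

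**Analysis.** The SAP's Statistical Methods paragraph gives one method, for the surgeon and patient questionnaires: "a Wilcoxon test will be performed for each answer against a theoretical median of 4.0 (best"). It reasons that needle insertion should have little bearing on how the whole operation turns out, and then fixes the control arm too: "the standard of care is assumed to provide the current best care, so its theoretical median should be 4.0".

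**Stated aim.** The SAP's sample-size paragraph says there was no power calculation. It nevertheless calls 15 per group enough to judge bruising and "the ability of the TPAD device to function as intended as compared to the control group".

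Neither document gives a between-arm method for any endpoint. Neither gives any analysis method for access time, bruising or adverse events.

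**The concern.** A test against a fixed theoretical median is a one-sample test and cannot be read as a rank-sum test between arms. Whether controls score 4.0 is something this trial can observe, yet the SAP assumes the answer. That leaves the randomised control data with no role in the analysis.

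Placing the reference at the top of the scale adds a second problem. Every departure from 4.0 is downward, so the test can only detect imperfection. A TPAD arm that scores clearly better than control can be reported as significantly below standard, and one that scores worse can escape notice. Running the same test in each arm does not help. The SAP gives no rule for reading the two results together, so any statement about TPAD versus control would rest on setting one p-value beside another.

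**Working it through.** **The plan's own figure.** The 15 per group has no alpha, power, effect size, SD or event rate behind it, so there is nothing to reproduce. The protocol's sections 1a and 2g give 10 per arm, so both sizes are shown below.

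**Assumptions.** The documents give no alpha, sidedness, test version, response distribution or questionnaire. I take 4.0 as the maximum because the SAP labels it best, and use an exact signed-rank test, zeros dropped, two-sided 0.05. All figures are illustrations.

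**The test at the ceiling.** Let k be the number of answers below 4. All k non-zero differences are negative, which is the most extreme of 2^k sign patterns. Hence p = 2 × 0.5^k:
- k=5: 2/32 = 0.0625
- k=6: 2/64 = 0.031
- k=14: 2/16384 = 0.0001

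An arm is flagged when k ≥ 6, whatever the other arm scores.

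**1. TPAD better but flagged.** Below best: 6/15 TPAD, 14/15 control.
- Plan: TPAD p=0.031, control p=0.0001. Both are flagged.
- Fisher, two-sided: 2 × [C(15,6)·C(15,14) + C(15,5)·C(15,15)] / C(30,20) = 156156 / 30045015 = 0.005, in TPAD's favour.
- Probability of superiority, if each shortfall is one point: (9/15)(14/15) + ½[(9/15)(1/15) + (6/15)(14/15)] = 0.56 + 0.207 = 0.77.

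**2. TPAD worse but not flagged.** Below best: 5/10 TPAD, 0/10 control.
- Plan: TPAD p=0.0625.
- Fisher: 2 × C(10,5)/C(20,5) = 504/15504 = 0.033.
- At 5/15 v 0/15: plan 0.0625, Fisher 2 × 3003/142506 = 0.042.

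**3. Identical arms.** Let q be the true share of answers below best, r = P(Bin(n,q) ≥ 6) the chance that one arm is flagged, and 2r(1−r) the chance that exactly one of the two is.

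| q | r, n=10 | exactly one, n=10 | r, n=15 | exactly one, n=15 |
|---|---|---|---|---|
| 10% | 0.00015 | 0.03% | 0.0022 | 0.4% |
| 20% | 0.0064 | 1.3% | 0.0611 | 11% |
| 30% | 0.0473 | 9% | 0.2784 | 40% |
| 40% | 0.1662 | 28% | 0.5968 | 48% |
| 60% | 0.6331 | 46% | 0.9662 | 6.5% |

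At q = 40% the true median is still 4, yet an arm of 15 is flagged about 60% of the time. With a one-sided 0.05 test (k ≥ 5), the last two quantities range from 0.3% to 46% (n=10) and 1.9% to 50% (n=15).

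**What a direct comparison could detect.** For a two-sample t-test at 80% power and two-sided 0.05, the detectable difference is about 1.32 SD at 10 per arm and 1.06 SD at 15.

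**The case against.** The strongest reply is that this is an unpowered pilot whose protocol objective is device feasibility, with no between-arm hypothesis. Benchmarking against a target is a recognised pilot design. The SAP's comparative wording concerns bruising and device function, whereas the Wilcoxon test concerns questionnaires, so linking the two is an inference.

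Some of this stands. The link is inferred, though section 2g does measure feasibility by questionnaire. For bruising, the fault is a missing method, not a wrong test. A pilot needs no powered test, and two-arm estimates with intervals would be enough; the SAP states neither. Randomising and surveying controls also has little purpose if their scores are then assumed.

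The numerical objections are partly right.
- Example 2 depends on the test version. For five tied one-point shortfalls the statistic is 7.5 from its mean, with SD √11.25 = 3.354. The normal approximation then gives p=0.025, or 0.037 with continuity correction; the one-sided exact p is 0.031. TPAD is flagged under each of these, so the claim that a worse TPAD arm can pass holds only for the exact two-sided test.
- Example 1 does not depend on the version: the one-sided exact p for k=6 is 0.016.
- The identical-arm figures are small when nearly all answers are at 4. They are error rates only if a reader treats one significant arm as a difference, a rule the SAP does not state.

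**Conclusion.** The concern holds and must be fixed. Followed as written, the plan gives no valid TPAD-versus-control result on the primary endpoint or any other, although it randomises a control group and claims a sample adequate for that comparison.

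This conclusion follows from the text alone and needs none of the illustrative figures. The ceiling argument additionally assumes that 4.0 is the maximum score. How often the plan would mislead in practice cannot be fixed, because the response distribution, alpha and test version are not stated. Across the assumptions shown, exactly one of two identical arms is flagged in anything from 0.03% to 50% of trials per item. The missing methods for access time, bruising and adverse events are a related but secondary gap.

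**What to change.** Drop the assumption that control sits at 4.0, make the between-arm comparison the stated analysis, and label every comparison exploratory.

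- **Questionnaire items answered in both arms:** exact (permutation) Wilcoxon rank-sum test, with the probability of superiority or a shift estimate and its 95% CI. Answers bunched near the top will often give a shift of zero, so the probability of superiority is the more informative choice. Name one primary item or score.
- **Items only TPAD cases can answer:** descriptive summary.
- **Bruising and adverse events:** risk difference with exact 95% CI.
- **Access and trocar-placement times:** Hodges-Lehmann difference with 95% CI, provided both arms are timed with the same start and stop points. Section 2a says only that "The time needed to obtain laparoscopic access and the time needed for trocar placement will be recorded", while section 2g ties the outcome to the device: "Secondary outcome measures include the time needed to obtain laparoscopic access using the device". The protocol should confirm that controls are timed. If control times do not exist, describe TPAD times only.

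The SAP should also acknowledge that surgeons know the arm and that one surgeon may complete several questionnaires.

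**Cost.** For questionnaires, bruising and adverse events: SAP wording and a few lines of code. Access time needs a protocol line as well, and control times that were not recorded cannot be recovered. Precision will be low, with 80% power only for differences of about 1.1 to 1.3 SD, so the results estimate rather than confirm.

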### b. Objectives

We hope to assess device feasibility and efficacy of the Tautona TPAD for clinical use.

---

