### c. Rationale for Research in Humans

The purpose of the study is to measure ease-of-use by surgeons in human patients. therefore, human patients are needed.

---

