**a. Past Experimental and/or Clinical Findings**

Gaining laparoscopic access to the abdomen is a clinical challenge due to the nature of inserting surgical instruments through small incisions. Laparoscopic entry is a blind procedure and thus it is not surprising that at least 50% of major complications of laparoscopic surgery occur prior to the commencement of the intended surgery. This complication rate has remained stable for the past 25 years. The Hasson technique (open) is considered safer, but is more time consuming with an average access time of 3-10 minutes (Hasson 1999). The Veress technique is a blind technique that has the advantage of being faster, however carries a risk of major vascular injury during insertion (Sangrasi et al, 2011). It is critical during

Veress needle access to upward tension on the abdominal wall so as to increase the distance between the abdominal wall fascia and major abdominal blood vessels. In order to address this need, Tautona developed the TPAD, a device which applies suction to the abdominal wall skin to facilitate easy upward traction during Veress needle insertion, thus improving speed and safety of peritoneal access.

Sangrasi et al. A safe quick technique for placement of the first access port for creation of pneumoperitoneum. Journal of the Society of Laparoscopic and Robotic Surgeons. 2011

Hasson HM. Open laparoscopy as a method of access in laparoscopic surgery. Gynaecol Endosc. 1999;8:353–62.

---

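### The questionnaire tests against 4.0, the best score, can show only a shortfall and cannot support a claim that the TPAD is easier than, equivalent to or better than standard entry

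*SAP*

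**What the plan says.** The protocol (Study Endpoint(s)) makes the surgeon questionnaire primary: "The primary outcome measure is device feasibility as measured by a surgeon questionnaire, which is completed at the end of every surgery". The stated aims go beyond feasibility. Rationale for Research in Humans says "The purpose of the study is to measure ease-of-use by surgeons in human patients", and Objectives says "We hope to assess device feasibility and efficacy of the Tautona TPAD for clinical use". The background (Past Experimental and/or Clinical Findings) describes a device meant to "facilitate easy upward traction during Veress needle insertion, thus improving speed and safety of peritoneal access". Patients are randomised in blocks to TPAD or standard of care.

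The SAP (Statistical Methods) plans one kind of analysis for the questionnaires: "a Wilcoxon test will be performed for each answer against a theoretical median of 4.0 (best"). Its reason for that reference value begins "Since the insertion of the Veress needle should not significantly impact the final outcome of the entire laparoscopic procedure". It then places the control arm at the same value: "the standard of care is assumed to provide the current best care, so its theoretical median should be 4.0". It specifies no between-arm test of the questionnaire, although its sample-size paragraph speaks of judging device function against control.

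**The concern.** The reference value is the best available answer, and the control arm is assumed to have its median there. A test against the top of a scale works in one direction only: it can find that answers fall short and cannot find that they are good. No TPAD median can exceed the assumed control median.

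What is at stake is how the primary result is read. A non-significant test against 4.0 could be taken to mean that the TPAD matches standard care, or that the efficacy objective was met. Neither follows. The randomised control arm, which could inform such a statement, has no role in the planned questionnaire test.

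**Working it through.** **Inputs.** From the SAP: one-sample Wilcoxon test, reference 4.0 (best), assumed standard-of-care median 4.0, 15 per group. From the protocol: the study ends at 10 per arm, while planned enrollment is 30 (2 × 15). Both sizes are used below. The SAP says the size is not based on power and gives no significance level or effect size, so its 15 cannot be reproduced. Assumptions made here: 4 is the highest score; two-sided 5% level; the test is run within an arm.

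**1. The planned test.** With k answers below 4 and the rest at 4, the zero differences drop out and all k remaining differences are negative. The exact two-sided p is 2/2^k:

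- k = 5: 2/32 = 0.0625
- k = 6: 2/64 = 0.031

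Significance therefore needs at least 6 answers below 4, and it always points against the arm tested. The one-sided p in the favourable direction is 1.0 whatever the data. If all answers are 4, the best possible result, no differences remain to rank.

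**2. What a non-significant result leaves open.** If a share π of TPAD answers is below 4, the chance of significance is P(Binomial(n, π) ≥ 6):

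| π | n = 10 | n = 15 |
|---|---|---|
| 0.2 | 0.006 | 0.061 |
| 0.3 | 0.047 | 0.278 |
| 0.4 | 0.166 | 0.597 |

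With 40% of answers short of best, the test is non-significant 83% of the time at n = 10 (1 − 0.166) and 40% at n = 15 (1 − 0.597).

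**3. A direct comparison, best case for the TPAD.** Let every TPAD answer be 4 and let q be the share of control answers at 4. The probability that a TPAD answer beats a control answer, counting ties as half, is (1 − q) + q/2 = 0.5 + 0.5(1 − q).

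For 4 versus below 4, Fisher's exact two-sided p with k control answers below 4 and no TPAD answers below 4 is 2·C(n,k)/C(2n,k):

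- n = 10: k = 4 gives 2 × 210/4845 = 0.087; k = 5 gives 2 × 252/15504 = 0.033
- n = 15: k = 4 gives 2 × 1365/27405 = 0.100; k = 5 gives 2 × 3003/142506 = 0.042

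Five control answers below 4 are needed at either size, so power is P(Binomial(n, 1 − q) ≥ 5). For n = 10 and q = 0.5 this is 638/1024 = 0.623.

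| q | Largest P(TPAD better) + ½ ties | Power, 10 per arm | Power, 15 per arm |
|---|---|---|---|
| 0.5 | 0.75 | 0.623 | 0.941 |
| 0.6 | 0.70 | 0.367 | 0.783 |
| 0.7 | 0.65 | 0.150 | 0.485 |
| 0.8 | 0.60 | 0.033 | 0.164 |
| 0.9 | 0.55 | 0.002 | 0.013 |
| 1.0 | 0.50 | 0 | 0 |

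**4. Sensitivity.** A Mann-Whitney test that uses all four levels does better. With scores below 4 split 60/30/10% over 3, 2 and 1 (20,000 simulated trials), power at 10 / 15 per arm is 0.83 / 0.98 at q = 0.5, 0.35 / 0.70 at 0.7, 0.12 / 0.35 at 0.8 and 0.01 / 0.05 at 0.9. In the other direction, if only 95% of TPAD answers are 4 and q = 0.5, Fisher power falls to 0.43 / 0.74.

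**The case against.** A reader might infer that the questionnaire has no room above control at all, so that it could not register easier entry even if the arms were compared directly, and that a helpful device and an inert one would give the same ratings. The documents do not support that. A median of 4.0 on a scale that stops at 4 needs only about half the control answers to be 4, and at that point a direct comparison has 62% / 94% power in the best case. Power is zero only if every control answer is 4, which the SAP does not say. The 4.0 is also a reference value for a test, not an observation. If control answers turn out lower, there is more room.

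Other points on that side also stand. The form is not shown, so the scale maximum, the number of levels and the items are inferred or unknown. The study is an unpowered pilot, its primary outcome is called feasibility, and no superiority hypothesis on ease is stated. For feasibility, asking whether ratings fall short of best is defensible. A reader might also infer that the trial cannot address efficacy at all. But Objectives does not tie efficacy to the questionnaire, and the endpoint section adds measures without this ceiling: "Secondary outcome measures include the time needed to obtain laparoscopic access using the device, as well as monitoring for adverse events".

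None of this rescues the planned test as support for a favourable claim. It limits the point to what the tests against 4.0 can be used to say.

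**Conclusion.** The point holds in this form. If 4.0 is the scale maximum, the planned one-sample tests can show only a shortfall and can never favour the TPAD. Non-significance is weak evidence: it leaves open a 40% share of answers below best with probability 83% at n = 10 and 40% at n = 15. A between-arm comparison could show improvement, but only through control answers below 4. Its exact power in the best case runs from 62% / 94% with half of the control answers at 4 to 3% / 16% at 80% and 0.2% / 1.3% at 90%.

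These figures rest on the assumed control distribution, a two-sided 5% level and, for the exact test, scoring as 4 versus below 4. The defect concerns claims about ease of use and efficacy drawn from the questionnaire. It does not invalidate the feasibility pilot.

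**What to change.** In the SAP:

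1. State that the tests against 4.0 can show only a deficit and that, whatever their result, they cannot support a claim that the TPAD is easier than, equivalent to or better than standard entry.
2. For each item answered in both arms, report the full distribution by arm, including the share below 4, with a between-arm comparison and confidence interval. The difference in the share at 4, or the probability that a TPAD answer is better (ties counted half), would serve.
3. Base any statement of improvement on that comparison and on access time compared between the randomised arms. The SAP gives no analysis of access time, and the endpoint wording refers to time with the device, so confirm that access is timed in control patients too.

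The cost is a few sentences and one table, with no extra patients, visits or procedures. The price is a more limited conclusion, and intervals will be wide at 10 or 15 per arm.

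Optional, if collection is still open: add an ease-of-entry item in both arms with room on either side of usual entry, for example −3 (much harder) to +3 (much easier). Its downside is real. It is an unvalidated judgement by surgeons who know which method they used, and control answers would be expected near 0 because usual entry is being compared with itself.

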Patients will undergo routine postoperative care as indicated by their surgery. no additional visits will be required due to their being enrolled in the study. The patient will participate in a questionnaire and may take non-identifiable photographs of the portion of the patients skin where the TPAD device acts, as described above.

---

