**d. Study Conclusion**

The experiment terminates for each participant at the end of their surgery. no additional follow up is needed. the general surgery service will care for the patients post-operatively and manage any adverse events that may occur.

---

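### The protocol stops the study at 10 patients per arm, but the SAP's size statement is for 15 per group, and nothing reconciles the two

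*SAP*

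**What the plan says.** Four places bear on the size of the trial.

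- **Protocol 1.a, Brief Summary.** Ten patients are to have surgery with the device, and "Ten patients will undergo standard of care without use of the TPAD device".
- **Protocol 2.g, Study Endpoint(s).** "The study will terminate after 10 patients have been enrolled and have undergone surgery with use of the study device" and 10 have had standard of care and completed the survey. The same section separately lets the project leader modify or end the study for lack of feasibility or for dangerous device-related events.
- **Protocol 8.a, Planned Enrollment.** Items (i) and (ii) each show 30. The labels of these items do not appear in the text.
- **SAP, Determination of Sample Size.** "There were no statistically powered sample size requirements for this study". The next sentence says that "the sample size of 15 for each group would be sufficient to determine bruising" and to show, against control, that the device works as intended.

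On bruising, protocol 9.a lists it, together with skin discoloration, as the risk of the device itself. The secondary outcomes in 2.g include the access time "as well as monitoring for adverse events". Section 2.a adds "Any adverse events will be recorded by medical record review" and foresees "non-identifiable photographs of the portion of the patients skin where the TPAD device acts". The only analysis in the SAP is a Wilcoxon test of each questionnaire answer against a median of 4.0.

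**The concern.** A count that ends a study and the sample size in its SAP should be the same number, or the plan should say why they differ. Here they differ by 5 per arm.

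If the team follows protocol 2.g, the SAP's only statement about size describes a study that was not run, and nothing is said about what 10 per group can show. If the team follows the SAP, patients are treated beyond the protocol's own stopping count, some of them with an investigational device. In either case, a later reader cannot tell from the documents whether the final number was planned or was settled after data had been seen.

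A smaller matter sits in the same SAP sentence. It claims sufficiency for bruising compared with control, but gives no bruising rate, no precision target and no bruising analysis from which that could follow.

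**Working it through.** **1. Is there a calculation to reproduce?** No. The SAP says the size was not powered and gives no significance level, power, effect size, event rate or dropout allowance. The figure of 15 per group cannot be rebuilt by any formula, so the check is whether the stated sizes agree.

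**2. Totals**

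| Source | Per arm | Total |
|---|---|---|
| Protocol 1.a | 10 and 10 | 10 + 10 = 20 |
| Protocol 2.g (stopping count) | 10 and 10 | 10 + 10 = 20 |
| Protocol 8.a | not given | 30 |
| SAP | 15 and 15 | 15 + 15 = 30 |

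The gap is 30 − 20 = 10 patients, or 5 per arm. Relative to 30, the smaller study is 10/30 = 33% short. Relative to 20, the larger study is 10/20 = 50% bigger.

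**3. Can an allowance for loss bridge the gap?** Suppose 30 are enrolled so that 20 count. The required loss is 1 − 20/30 = 33%. No section states such an allowance, and active participation is given as less than one day (8.m). This reading also leaves the SAP unexplained, because the SAP gives 15 per group as the sample size and not as an enrolment figure.

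**4. What the two sizes mean for bruising.** This is for orientation only. Assume that every device patient counted was actually examined for bruising and that none had any. The exact (Clopper-Pearson) two-sided 95% upper limit for 0 of n is 1 − 0.025^(1/n):

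- n = 10: 1 − 0.025^(1/10) = 0.3085, that is 30.8%.
- n = 15: 1 − 0.025^(1/15) = 0.2180, that is 21.8%.

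The difference is 9.0 percentage points. The documents give no bruising rate, so the chance of seeing at least one case, 1 − (1 − p)^n, is shown for a range of assumed true rates p:

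| Assumed rate | n = 10 | n = 15 |
|---|---|---|
| 5% | 40% | 54% |
| 10% | 65% | 79% |
| 20% | 89% | 96% |

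Whether either size is sufficient therefore depends on a rate and a target that the SAP does not state. These are device-arm figures and do not measure the comparison with control that the SAP sentence mentions.

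**The case against.** The strongest reply is that this is an openly unpowered pilot. The planned Wilcoxon tests are not said to depend on 15 per group, and saying that 15 would be sufficient does not say that 10 would not be. That stands: no harm to the questionnaire analysis has been shown, and none is claimed here.

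A second reply is that Planned Enrollment may be only a ceiling. With its item labels not visible, that section taken alone could be read so. This weakens it as evidence of a 30-patient target but leaves the SAP's 15 per group against the protocol's 10.

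A third is that the SAP, dated August 19, 2024, may be the later text. Neither document says that one supersedes the other, and the visible protocol text carries no date to compare.

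A reader might also infer more than the documents support:

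- *That the sample size was miscalculated.* No calculation exists to be wrong.
- *That the count in 2.g is the only way the study can end.* The project leader's discretion in the same section is another. It does not reconcile 20 with 30.
- *That bruising cannot be captured, or that the sufficiency claim is false.* Record review and skin photographs are both foreseen. The claim is unsupported, which is a weaker criticism.

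**Conclusion.** The point holds as a conflict between stated sizes. Protocol 1.a and 2.g give 20 patients, the SAP gives 30, and Planned Enrollment shows 30. The protocol's stopping count and the SAP's group size cannot both be followed. The difference is 10 patients: one third fewer than the SAP describes if the study stops at 20, or 10 beyond the protocol's count, 5 of them with the device, if 15 per arm are treated. This rests only on the current wording of the two documents. They do not show which size is intended.

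The bruising claim is a secondary defect: it is stated without a basis. The limits of 30.8% and 21.8% assume no bruising and complete assessment of 10 or 15 device patients. With fewer assessed, the limit would be higher.

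**What to change.** **Size.** Choose one number per arm without reference to accrued results, and make protocol 1.a, 2.g and 8.a and the SAP agree.

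- If 15 per arm is meant, change the counts in 1.a and 2.g.
- If 10 per arm is meant, change the SAP, and change or explain the 30 in 8.a.
- If 30 is only an enrolment ceiling, say so in 8.a.

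**SAP sufficiency sentence.** Replace it with text such as:

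> The size is not powered for differences between arms. Bruising will be reported by arm as the number of patients with bruising among those actually assessed for it, with exact two-sided 95% confidence intervals.

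The denominator should be the patients assessed. A record that is silent on bruising is not an assessment, and counting it as one would make a zero look more reassuring than it is. For the same reason, do not fix the denominator at 10 or 15 in advance.

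**Cost.** Text edits and one short descriptive table. Choosing 15 per arm permits 10 more patients than the stopping count in 2.g now does. Choosing 10 per arm accepts the wider interval: with no bruising and all assessed, an upper limit of 30.8% instead of 21.8%.
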